6.2.2 Consent and First Screening/Baseline Assessment

The following procedures will occur at the first screening/baseline assessment appointment to determine eligibility:

- i. Informed consent/assent: The purpose, all testing procedures, program components and randomization will be reviewed by a trained member of the study team, in detail, at each respective site. Potential participants will be informed of the possible risks, inconveniences, benefits, and right to withdrawal. All participants and parents/guardians will sign COMIRB-approved consent/assent forms. In the event of a remote visit, e-consent will be obtained using REDCap and explained via secure video software or by phone. In the event that any changes are made to the consent/assent form(s) that require participants and parents/guardians to be re-consented, a member of the study team will explain the change in detail and have participants and parents/guardians sign a new copy of the updated consent/assent forms before further study procedures occur.
- ii. BMI indices: BMI (kg/m^2) will be derived from height by stadiometer and weight by calibrated digital scale. BMI $\%ile^{137}$ will be computed to estimate eligibility (≥ 85 percentile). If this initial screening/baseline visit is completed remotely, participants and parents/guardians will be provided with CDC instructions for obtaining an accurate height and weight, which will be used to estimate eligibility. These estimates will provide a reasonable estimate of whether youth will meet the BMI eligibility criterion. Using this approach in our other studies (e.g., COMIRB Protocol #16-2571), 100% of youth meet the BMI criterion at the second screening visit. The fasting measurement of weight and measured height collected at the second laboratory screening/baseline visit will be used to compute baseline BMI indices and

to determine final eligibility for this criterion.

- iii. Medical and family history: A brief psychiatric and medical health history, including T2D, prediabetes, and gestational diabetes, of the participant and family will be conducted with a parent/guardian by a trained research staff member. Psychiatric history includes parent and teen report of any mental health diagnoses that could be exclusionary; if the family reports a current mental health diagnosis (e.g., anorexia nervosa, bipolar disorder, bulimia nervosa, conduct disorder, MDD with high acuity, obsessive compulsive disorder, panic disorder, posttraumatic stress disorder, psychosis, and substance/tobacco/alcohol use disorder), a psychologist will speak with the family for further assessment and follow-up/referrals (and exclusion), as indicated. Eligibility based upon at least one first- or second-degree relative will be determined, as well as medication status. As in our other studies,^{119,138} females will report whether they are or suspect that they could be pregnant. Pregnant females will not be included.
- iv. Psychopathology: The Schedule for Affective Disorders and Schizophrenia for School-Age Children (K-SADS) – Computerized Version¹³⁹ Suicidality and Self-Harm module will be administered to determine if adolescent girls and boys report depression acuity that, in the opinion of the study investigators, would warrant study exclusion and necessitate a referral for more intensive treatment. Any participant with current active suicidal ideation or self-harm, regardless of degree of mood concerns, will be referred for treatment (and excluded). If the screening visit is completed remotely, a parent or guardian will be asked to be in the home and accessible for the duration of the completion of the K-SADS to ensure access for communication of any safety concerns. Additionally, the interviewer will confirm the child's physical location prior to starting the interview. Written remote safety protocols have been developed in the event that suicidal ideation or other risks concerns arise.
- v. Physical exam/puberty staging: Physical exam, including puberty staging as well as review of vitals, blood pressure, and waist circumference, will be conducted to evaluate adolescent health status. Exam may take place during either the first or second screening visit based on participant and provider availability.

6.2.3 Second Screening/Baseline Assessment

For the second screening/baseline assessment, participants will be asked to arrive for a morning appointment at the Pediatric CTRC at Children's Hospital Colorado, the Human Performance and Clinical Research Laboratory at Colorado State University, the Military Cardiovascular Research Outcomes Program at the Uniformed Services University, or the Children's Research Institute at Children's National Medical Center. They will be asked to observe a 10-hour overnight fast, meaning nothing to eating or drink other than water from ~10:00pm the night prior and the morning of their appointment. The following measurements to determine eligibility will be collected at this visit:

- i. BMI indices: BMI (kg/m^2) will be derived from measured height in triplicate by stadiometer and fasting weight by calibrated digital scale. BMI z-score and BMI %ile¹³⁷ will be computed to determine eligibility (≥ 85 percentile).
- ii. Physical exam/puberty staging: Physical exam including blood pressure in triplicate and waist circumference will be conducted to evaluate adolescent health status. Exam may take place during either screening visit 1 or 2 based on participant and provider availability.
- iii. Insulin resistance: Oral glucose tolerance tests (OGTTs) are a well-validated, yet far

more practical and less invasive, costly, and labor-intensive method than clamps or intravenous glucose tolerance testing, while still permitting screening for T2D.¹⁴¹ Following a 10-hour overnight fast, participants will receive 1.75 g/kg of glucola (max=75g). Blood will be sampled for insulin and glucose at fasting and 2-hours. Insulin resistance will be estimated from fasting insulin and glucose with the homeostasis model assessment of insulin resistance (HOMA-IR),¹⁴² and we will calculate insulin sensitivity index (ISI) using fasting and 2-hour insulin and glucose.¹⁴³ Extant data suggest that ISI may yield more valid estimates of insulin sensitivity than HOMA-IR alone.¹⁴⁴⁻¹⁴⁷ OGTT is well validated in youth, practical in large pediatric cohorts, and shows excellent convergence with estimates derived from more frequent sampling methods.^{143-145,148,149} While for research purposes, blood will be processed and frozen until processing by the University of Colorado Core Laboratory for estimation of insulin/glucose to compute HOMA-IR and ISI metrics, fasting glucose and two-hour glucose will be checked at the visit, directly after each respective draw, for eligibility using an automated point-of-care device (e.g., StatStrip). If blood cannot be obtained with venipuncture, blood will be drawn using a finger prick by lancet to determine eligibility. Individuals with impaired fasting glucose (fasting glucose ≥ 100 mg/dL), impaired glucose tolerance (2-hour OGTT glucose ≥ 140 mg/dL), or with values potentially suggestive of T2D (fasting glucose ≥ 126 mg/dL or 2-hour OGTT glucose ≥ 200 mg/dL) will be notified and referred to their physician.

6.2.4 Enrollment, Baseline, and Randomization

Enrollment

This study uses a single informed consent form (for both parent/guardian and adolescent minor), that describe both the screening evaluations and the study procedures. Children's National Medical Center has a site-specific consent form and a separate site-specific assent form, reviewed and signed by the parent/guardian and adolescent, respectively. We will track the number of parents/participants who sign consent forms. "Enrollment" will be defined as the date of randomization. The enrollment date will be recorded on a case report form.

Baseline Assessments

As part of the screening process, adolescents will complete measures across both screening study visits. Measures may be completed at either visit or remotely, unless otherwise listed (e.g., Food Preferences Questionnaire).

- i. Adolescents will report eating in response to negative affect on the Emotional Eating Scale-Adapted for Children (EES-C).¹⁵⁰ Youth rate the frequency of coping with negative affect in response to depression, as well as anxiety/anger/frustration and feeling unsettled. This measure shows good internal consistency, test-re-test reliability, discriminant and convergent validity,¹⁵⁰ including with our laboratory test meal studies.⁸⁶ Adolescents also will complete the Reward-Based Eating Drive Scale (REDS), a reliable/valid survey instrument of hedonic eating.^{151,152} Participants will complete these surveys via REDCap.
- ii. Theoretical therapeutic mechanisms: Adolescents in all conditions will complete four baseline surveys to measure theoretically informed therapeutic mechanisms underlying MBI and CBT. All adolescents will complete the Mindful Attention Awareness Scale (MAAS).¹⁵³ They also will complete the 20-item short form of the Five Factors of Mindfulness Questionnaire (FFMQ).¹⁵⁴ Parents will describe their adolescents on the Behavior Rating Inventory of Executive Functioning (BRIEF), assessing everyday

behavioral problems related to poor self-monitoring, emotional control, and related elements of executive dysfunction.¹⁵⁵ Adolescents will report frequency of negative and positive thoughts on the Children's Automatic Thoughts Scale-Negative/Positive.^{156,157} They will describe frequency and perceived pleasantness of social and physical activities on the Pleasant Events Schedule (PES).¹⁵⁸

- iii. Socioeconomic status: Parents will report on a number of standard demographic and socioeconomic factors that are indicators of the multifaceted construct of socioeconomic status (SES), including items from the Hollingshead Index,¹⁵⁹ the MacArthur Scale of Subjective Social Status,¹⁶⁰ and the Household Food Insecurity Access Scale.¹⁶¹

In addition to the screening evaluations described in **section 6.2.1**, the following baseline assessments will be collected:

Screening Visit 1

At the first screening visit, which will take place either remotely or in-person, the following additional survey will be given:

- i. Food Preferences Questionnaire: Participants will be asked to rate how much they like or dislike the foods that will be served during the laboratory eating paradigm (see below). We will assess average liking of lunch meal foods and average liking of snack foods, as well as the percentage of foods that were rated as "liked" (>5 on a Likert Scale from 1=I hate the food to 10=I love the food) for the lunch meal foods and for the snacks.

Baseline ambulatory home assessments

Adolescents will complete the following assessments in between the first screening visit and the second screening visit; adolescents will be offered an opportunity to re-wear/recollect home measures after the second screening visit, if they are non-compliant, in order to minimize missing data:

- i. Stress-related behavior: Physical activity: Habitual activity will be measured with the ActiGraph GT3X accelerometer (ActiGraph, Pensacola, FL), a lightweight monitor with well-established validity, reliability, and low reactivity in diverse child and adolescent samples for over 10 years.³ Adolescents will wear the monitor on their right hip during waking hours for 7 days. Consistent with recommended protocols, devices will be set to record with a 30 Hz sampling frequency and analyzed with 15-second epochs throughout the wear period. Adolescents will be given a log to record wear. Data will be reduced manually with data output and logs to delete non-wear periods. Following expert recommendations, data recorded on the first/last day will be discarded for incompleteness and possible reactivity on day 1. Adolescents with ≥4 complete days of data, including 1 weekend day will be retained in analyses.^{192,193} Mean ActiGraph counts/minute will be classified as moderate-to-vigorous or sedentary time according to validated count thresholds determined by Evenson et al.¹⁹⁴ and validated in youth.^{195,196} ActiGraph offers the advantage of characterizing the entire picture of habitual physical activity, including MVPA and sedentary time.
- ii. Stress-related physiology: Cortisol diurnal rhythm: Cortisol awakening and diurnal rhythm will be assessed with saliva collected in the home on 1 weekday and 1 weekend day.²⁰⁰ Samples will be obtained with an oral swab under the tongue for 120 sec at awakening, 2, 15, 30, and 45 minutes after awakening, 4:00 pm, and bedtime.^{201,202} Adolescents will be instructed to refrain from eating/drinking (other than water) until after the 45-minute sample and for 15 minute prior to afternoon/bedtime samples. As in our

past studies, the use of a participant log, phone/text reminders, and alarms will be used to support adherence. We will use color-coded screw-top bottles that record opening times to improve accuracy of collection timing, given its high importance.²⁰¹ Salivary cortisol is a well-accepted non-invasive indicator of circulating physiologically active free plasma cortisol.²⁰³ Latent growth models will model non-linear change in cortisol across 2 days as awakening response and diurnal rhythm.²⁰²

Screening Visit 2

At the second screening visit in the laboratory, the following additional baseline assessments will be evaluated:

- i. Pubertal staging: As puberty is related to insulin resistance,¹⁸ Tanner staging for breast and pubic hair (females) and testicular volume and pubic hair (males) will be performed by a trained medical provider. To accommodate medical provider schedules and participant/family schedules, pubertal staging may be carried out at screening visit 1 instead. Additionally, Tanner stage will be collected through adolescents' self-report on a validated questionnaire.¹⁶² Participants will be asked to define their physical development based on illustrations of their external characteristics, which corresponded to Tanner stages 1-5 of breast and pubic hair development for girls and Tanner stages 1-5 of testicular volume and pubic hair development for boys.
- ii. Body composition: During a fasted state, fat/fat-free mass will be assessed via air displacement plethysmography (BodPod), which shows good test-retest reliability and convergence with dual energy x-ray absorptiometry,¹⁶³ but is far more cost-effective.
- iii. Stress-related behavior: Several measures of hedonic eating, referring to eating for reward/pleasure as opposed to physiological hunger,⁷⁵ will be collected. The overeating section of the Eating Disorder Examination (EDE), a semi-structured interview, will be administered by a trained research assistant to identify frequency of 3 types of eating episodes: objective binge (overeating with loss of control), subjective binge (loss of control without objective overeating as assessed by the interviewer, but viewed as excessive by the interviewee), and objective overeating (overeating without loss of control). Tests of the EDE's discriminant validity, internal consistency, concurrent validity and test-retest reliability support its use in adolescents.¹⁶⁴⁻¹⁶⁶ The EDE may be conducted in-person during the screening visit, or alternatively, may be conducted remotely using secure video software or by phone.

A laboratory paradigm¹³⁸ will be used to observe eating in the absence of hunger, which we have shown is related to dispositional mindfulness in adolescents at risk for T2D.¹⁶⁸ After eating a lunch-type meal until no longer hungry, youth will eat *ad libitum* for 15 minutes from a large, palatable snack food array. Youth are instructed to taste and rate their preferences for the snack foods and then to consume as much as they would like. Activities (e.g., magazines, coloring sheets, handheld video game like a Nintendo Switch) are provided during the snack period. Snacks consumed are assessed as changes in weight (g) before-after eating, and total energy intake (kcal) in the absence of hunger is calculated using USDA National Nutrient Database for Standard Reference and nutrient manufacturer information.

- iv. Stress-related physiology: Adolescents will complete the Trier Social Stress Test,¹⁶⁹ involving a 10-minute speech and 4-minute mental arithmetic task in front of an

evaluator, which is known to induce a physiological stress response.¹⁷⁰ Blood pressure and heart rate will be monitored approximately every 3 minutes throughout the test and summarized as area under the curve. We have shown that dispositional mindfulness relates to adolescents' reactivity in this task.¹⁷¹

Randomization

Upon completion of all screening and baseline assessments, a research staff will notify the adolescent and their parent/guardian that they completed all screening and baseline assessments and are eligible. The ideal window is that screening/baseline assessments will occur within 12 weeks/3 months of the start of the intervention phase (first group session); we will allow for up to 6 months between screening/baseline and group initiation. In the event that more than 6 months transpires since the screening/baseline interval, all interested adolescents who appeared to be eligible or who had been determined to be eligible, will be invited to complete a re-screening, referring to a repeat of all screening/baseline assessments. Re-screening will only be offered if there is sufficient opportunity for the participant to take part in a subsequent intervention cohort (e.g., originally screened for cohort 1, but after >6 months, could be re-screened to be considered for participation in cohort 2). After all screening/baseline assessments are complete and prior to randomization, adolescents and parent/guardians will be asked to confirm their desire to continue to participate in the study. Adolescents and parents will each, independently report their preference for group condition (MBI, CBT, HealthEd, or no preference). Adolescents then will be randomly assigned to either a MBI, CBT, or HealthEd group using the RedCAP randomization module by the lead study coordinator. Date of randomization will be considered date of enrollment.

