6.2 Description of Evaluations

6.2.1 Phone Screening Evaluation

We will conduct a phone screen to estimate eligibility. The phone screen will estimate the inclusion criteria of: age, height and weight to estimate BMI percentile, and family history of T2D; and the exclusion criteria of: major medical problem and exclusionary medication use. At this stage, we also will have adolescents complete a REDCap survey of the CES-D depression measure to determine the inclusion criterion for elevated depression symptoms (CES-D total score >20). Adolescents who cannot easily access REDCap may be screened by CES-D interview (i.e., asking the questions by phone). We have used the same approach in previous studies (e.g., COMIRB protocol #16-2571). Using this approach, approximately 74% of adolescents who meet eligibility criteria by phone screen also meet eligibility criteria when they proceed to the consent and screening/baseline assessment phase.

Adolescents who appear to be eligible following the phone screening phase will be scheduled for a series of two screening/baseline assessment appointments. The first screening/baseline assessment may take place either remotely via secure video software/phone or in-person. The second screening/baseline assessment will be conducted in-person in the laboratory. Laboratory assessments will be collected at one of the four sites: (i) the Pediatric Clinical and Translational Research Center (CTRC) at Children's Hospital Colorado, (ii) the Human Performance and Clinical Research Laboratory at Colorado State University, (iii) the Military Cardiovascular Research Outcomes Program at the Uniformed Services University, or (iv) the Children's Research Institute at Children's National Medical Center. Ambulatory measures of physical activity and cortisol will be assessed in between the first and second screening/baseline appointments.

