7. RISK ASSESSMENTS

7.1 Risks

The risks associated with participation in the proposed study are consistent with IRB definitions of minimal risk. Participants and their parents/guardians will be informed in detail of all potential risks during the informed consent and assent process. We anticipate the follow risks:

- i. Physical examination: Physical examination by a licensed medical provider, including a physician or advanced practice provider, will be performed in a private examination room. Although appropriate measures will be taken to protect privacy, some adolescents may find this embarrassing.
- ii. Phlebotomy: We will draw a blood sample in a fasted state and two-hours after glucola administration. We will minimize the pain of blood drawing by offering the participant numbing cream prior to the blood draw. Blood will be drawn by venipuncture, but finger prick for point-of-care glucose assessment will be offered if blood cannot be obtained by venipuncture. Discomforts are common, but minor. In about one in 10 cases a small amount of bleeding under the skin will produce a bruise (uncommon risk). The risk of a blood clot forming in the vein is about one in 100, while the risk of infection or significant blood loss is one in 1000 (rare, but serious). Amount of blood withdrawal (no more than 3 tablespoons at the screening, and 3 tablespoons at each of the 2 follow-up appointments: 6-week and 1-year) is well below the NIH and pediatric IRB guidelines for a safe amount of blood withdrawal.
- iii. ActiGraph: This small device to measure moderate-to-vigorous physical activity and sedentary time will be worn on the hip for 7 consecutive days at the baseline period and again at the 6-week and 1-year follow-up intervals. Aside from the inconvenience of wearing the device and removing it during water-based activities (e.g., swimming), as well as the time required to complete the accompanying log to record activity, there is no risk involved with these devices.

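### Read literally, the ActiGraph day rule excludes a fully compliant adolescent who starts wear on a Sunday, and discarding the last day automatically leaves little slack for anyone else

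*Combined protocol and SAP*

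**What the plan says.** Section 6.2.4 (baseline ambulatory home assessments, physical activity) sets the wear period: "Adolescents will wear the monitor on their right hip during waking hours for 7 days". Section 7.1 adds that the days are consecutive and that the same collection is made at each assessment: the device is "worn on the hip for 7 consecutive days at the baseline period and again at the 6-week and 1-year follow-up intervals".

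Section 6.2.4 then gives two data-reduction rules. The first is that "data recorded on the first/last day will be discarded for incompleteness and possible reactivity on day 1". The second is that "Adolescents with ≥4 complete days of data, including 1 weekend day will be retained in analyses". Non-wear periods are removed by hand, using the device output and the participant's wear log.

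On timing, section 6.2.1 says only that "Ambulatory measures of physical activity and cortisol will be assessed in between the first and second screening/baseline appointments", and that "The first screening/baseline assessment may take place either remotely via secure video software/phone or in-person". No section fixes or rules out a weekday for the start of wear. At baseline, section 6.2.4 says that "adolescents will be offered an opportunity to re-wear/recollect home measures after the second screening visit, if they are non-compliant". Section 6.2.6 says that the ActiGraph is worn again at both follow-ups and states no re-collection offer there.

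**The concern.** The two reduction rules were not checked against each other over the calendar. Any run of seven consecutive dates holds one Saturday and one Sunday. If the run starts on a Sunday, they are its first and last days, and both are discarded. The weekend requirement then cannot be met however well the adolescent complies. The re-wear offer does not clearly help, because its trigger is non-compliance and it is written for baseline only.

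A second, milder effect applies to every start day. With five days left, a minimum of four allows one missed day. Of the two reasons given for the discards, reactivity is tied to day 1. The last day goes for incompleteness, which the device output and log can show case by case.

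What is at stake is valid data on physical activity. It is one of the stress-related behavior measures modelled over time in section 8.6.2, and those behaviors are proposed mediators of change in insulin sensitivity. A lost baseline record matters most, because the models adjust for the baseline value of the outcome.

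**Working it through.** The plan states no figure for this measure, so there is nothing to reproduce first.

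**Inputs from the documents.** Seven consecutive days (6.2.4, 7.1); first and last discarded (6.2.4); at least four complete days including one weekend day (6.2.4); 120 randomized, about 40 per arm (Précis, 8.3).

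**Inputs assumed.** Start-day distribution, and the probability *p* that a worn day is complete. The documents give neither.

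**Step 1: days kept, perfect wear.** Seven dates minus two leaves five.

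| Start | Days kept | Weekend days | Passes |
|---|---|---|---|
| Mon | Tue–Sat | 1 | yes |
| Tue | Wed–Sun | 2 | yes |
| Wed | Thu–Mon | 2 | yes |
| Thu | Fri–Tue | 2 | yes |
| Fri | Sat–Wed | 2 | yes |
| Sat | Sun–Thu | 1 | yes |
| Sun | Mon–Fri | 0 | no |

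A Monday or Saturday starter who misses one weekday still has four complete days including the weekend day, and passes. One missed day excludes them only if it is their single retained weekend day.

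**Step 2: numbers affected per assessment.** Count = 120 × share starting on Sunday.
- 0%: 0
- 2%: 2.4
- 5%: 6
- 10%: 12
- uniform, 1/7 = 14%: 120/7 = 17.1, or 40/7 = 5.7 per arm

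**Step 3: other ways of counting the days.** If wear runs from part-day to part-day and touches eight dates, six remain after both ends are cut. A Sunday start keeps Monday to Saturday and passes. Reading the slash as only one end dropped also removes the failure.

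**Step 4: cost of four of five, leaving Sunday aside.** Take Monday-to-Friday starts, with days independently complete with probability *p*, and *q* = 1 − *p*.

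- Two weekend days kept (Tue–Fri starts): any four of the five include a weekend day, so P = 5p⁴q + p⁵. At 0.85: 0.3915 + 0.4437 = 0.8352.
- One weekend day kept (Mon start): P = p(p⁴ + 4p³q). At 0.85: 0.85 × (0.5220 + 0.3685) = 0.7569.
- Average: (4 × 0.8352 + 0.7569)/5 = 0.820.
- Only day 1 dropped: each of these starts keeps six days with both weekend days. Of the 15 ways to have exactly four complete, one omits both weekend days, so P = 14p⁴q² + 6p⁵q + p⁶. At 0.85: 0.1644 + 0.3993 + 0.3771 = 0.941.

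| *p* | As written | Day 1 only dropped |
|---|---|---|
| 0.80 | 72% | 88% |
| 0.85 | 82% | 94% |
| 0.90 | 91% | 98% |

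The difference at 0.85 is 12 percentage points. It treats the last day as being as likely to be complete as any other, so it is an upper bound if devices are often taken off during that day. On the eight-date reading, the rule as written keeps the same six days for these starts and already reaches the right-hand column.

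**The case against.** The strongest reply is that the exclusion depends on how days are counted. Giving incompleteness as the reason for the discards suggests partial fitting and return days. If those lie partly outside the seven, the period touches eight dates and nobody is excluded by the calendar. That stands as a possible reading. But section 7.1 speaks of seven consecutive days, and neither section says that the discarded days are extra, so the count needs defining in any case.

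Sites may also avoid Sunday starts in practice, or offer re-wear to anyone whose record is invalid. Both are plausible, and neither is written.

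The discard rule is attributed to expert recommendations. That supports caution about day 1 and about partial days. It gives less support for removing a last day that device and log show to be complete.

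A reader might infer more than the documents bear:
- **That one collection in seven is lost.** This needs uniform start days, for which there is no evidence.
- **That only about 69% of records, and about a third of participants across all three assessments (0.694³ = 0.33), would be valid.** These figures combine uniform Sunday starts with an assumed 0.85 and independence across assessments. The mixed models in section 8.6.2 do not need all three time points.
- **That assessment feasibility would be understated.** Section 8.5.2 defines that endpoint as checklist accuracy, which valid accelerometer days do not enter.

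**Conclusion.** On the plain wording, the rule excludes a Sunday starter with perfect wear at that assessment, and only a Sunday starter. The number affected is unknown: 0 to about 17 of 120 per assessment, the upper figure assuming uniform starts, and none on an eight-date reading.

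On the same seven-date reading, discarding the last day automatically also lowers the chance of a valid record for weekday starts from 94% to 82% at an assumed daily completeness of 0.85. The direction does not depend on that assumption; the size does.

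The loss falls on a secondary, exploratory measure and proposed mediator. The primary outcomes in section 8.5.1 are untouched, and section 8.6.2 itself says that power for these analyses may be insufficient. Severity is minor. It is worth correcting because the change is small and, on any reading of the seven days, cannot discard valid data that the present rule keeps.

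**What to change.** In section 6.2.4 and the data-reduction procedure:

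1. Always discard day 1. Discard the last day only when device output and wear log show it to be incomplete.
2. State how the 7 days are counted: calendar dates or 24-hour periods, and whether fitting and return days are included.
3. Apply the same rule at baseline, 6 weeks and 1 year, including to records already collected. Fix it before database lock, and have it applied by staff blind to arm. Sections 3.9 and 8.4 make this possible: the principal investigator and statistician are blinded until lock, and outcome analyses wait for study completion.
4. For collections still to come, avoid Sunday starts or add one day of wear. With eight dates and both ends cut, every start day keeps at least one weekend day. The current version is dated October 2023 and section 3.6 expected enrollment to finish in July 2023, so this would mainly concern 1-year collections. An added day there would make wear length differ from earlier assessments; avoiding Sunday starts would not.

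The cost is a sentence or two of text and a completeness check on last days, using output and logs that are already reviewed by hand.
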